8.3. Patient Withdrawal from the Study and Replacement of Patients

A patient may be withdrawn from the study in the following cases:

- withdrawal of consent by the patient or his/her legal representative,
- study termination by the Sponsor.

If the patient or his/her legal representative withdraws his/her consent, no further evaluations will be performed, with the exception of safety data, which must be collected whenever possible.

If a patient decides to withdraw from the study, the reason must be recorded in the e-CRF. If a patient is withdrawn from the study due to an AE, all measures must be taken as needed to clearly document the outcome of the AE.

Data collected prior to withdrawal of the patient will be taken into account in the PK, efficacy and safety analyses.

Patients withdrawn from the study will not be replaced.

If a patient is lost to follow-up for reasons related to armed conflict, after several unsuccessful attempts have been made to contact him/her, and if no data are available after the treatment period, the patient will be removed from the primary analysis and another patient will be included.

8.4. Patients Lost to Follow-up

If a patient does not attend a protocol-planned visit, all necessary measures must be taken to contact him/her. In all cases, all necessary measures must be taken to document the outcome of the patient's condition, if possible.

9. Data Analysis and Statistical Methods

A draft of the full Statistical Analysis Plan (SAP) will be prepared prior to conducting the first FA. It will provide a more detailed description of the statistical methods. The SAP will be reviewed and, if necessary, amended prior to final database lock.

9.1. Sample Size Determination

The calculation of the sample size has been revised. The total size of the sample is now calculated to be 390 patients, instead of 510, with the same 2:1 allocation ratio, i.e. 260 patients in the fexinidazole group and 130 patients in the NECT group. If the expected success rates are 94% with NECT and 89% with fexinidazole³ then the power of the final analysis is 80% with an acceptability ("non-inferiority") margin of 13%. The calculations were made for a one-sided type-1 error of 0.025.

No provision will be made for patients lost to follow-up since the missing outcome will be imputed, except for patients in areas of armed conflict (see Section 8.3).

³ The observed response rate for NECT was as high as 0.97 in the per protocol population and 0.965 in the ITT population (43). However, the definition of success was not the same as in this protocol, and the success rate for NECT would have been 0.95 or 0.94 if the same definition had been used. If fexinidazole has the same true success rate as NECT, and is equal to 0.95 or 0.94, then the power of the study will be greater than 99%. However, NECT is a co-administration of two drugs and there is no reason to expect fexinidazole to be more effective than effornithine alone. Available data show that the success rate with effornithine depends on the project and ranges between 0.89 and 0.90. If the expectations are 0.90 for fexinidazole and 0.95 for NECT, the exact power of the final primary analysis is 91.6%.

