The primary analysis will be performed using a Blackwelder noninferiority test, based on the difference in the success rates at the Test-of-Cure Visit at 18 months with the maximum margin of noninferiority set at 13%.

The interim primary analysis will be performed using the same test, but with the timepoint of 12 months.

Sample Size

The sample size, initially calculated at 510 patients with statistical power of 87.9% has been reduced to 390 patients in total, with 260 patients in the fexinidazole group and 130 patients in the NECT group. Thus, the overall power is 80% if the actual success rate for NECT is 94% and 89% for fexinidazole.

Futility Analyses

Futility analyses will be performed in order to inform decisions about possible study discontinuation, based on pre-determined stopping rules. The aim is to limit the number of patients exposed to the investigational product in the event that the latter should prove to have limited efficacy.

Of note: data handling and data review will be performed in a blinded manner.

Interim Secondary Analyses

In the interim analyses, the success rate for NECT and for fexinidazole will be calculated on patients who have reached the 18-month follow-up visit and the rates will be compared to those calculated at the 12-month visit in the same patients.

The time course of the success rate will be analysed on the data available, using the same approach as for the final secondary analysis.

1. Background and Study Rational

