In life-threatening diseases, any margin of difference is clinically and ethically relevant, even if there may be differences in efficacy between treatments that are more or less interchangeable.

The observed absolute mean difference in the rate of favourable outcomes between the estimated treatment effects in various programmes/clinical studies is 17%. This would explain why a margin of 15% was used in a phase-III study on the efficacy of pafuramidine maleate (**Error! Reference source not found.**). B ecause products are not necessarily interchangeable, and efficacy is largely dependent on the project or programme, the margin of non-inferiority is not based on the limit of a non-pertinent difference, but rather on a difference in efficacy that is acceptable for an easily administered oral drug that can be used to treat HAT in primary healthcare facilities in outlying areas with little or no healthcare infrastructure (see Figure 4; p 107).

If the non-inferiority test is significant, this will not mean that fexinidazole is equivalent or superior to NECT, but rather that the practical advantage of an oral treatment counterbalances or outweighs a potential difference in efficacy in favour of NECT for the majority of experienced physicians. Interpretation of the size of the effect as concerns NECT and of the 95% confidence interval will prevail over interpretation of the test result in assessing the benefit-to-risk balance.

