An adjustment of the type-I error will be made in view of the interim analysis for success. The Pocock approach will be used to determine the threshold of significance of the interim analysis as well as that of the final analysis. As a reminder, the final analysis will be performed on the planned number of patients.

10. Independent Steering Committee/Data Safety Monitoring Board

An Independent Steering Committee (ISC or DSMB) composed of at least 3 members independent of the Investigators and the Sponsor, will be set up prior to study initiation. The ISC will monitor the study in order to minimise any risk of harm to the patients included in the study. At predetermined intervals, the ISC will analyse safety data and all information related to SAEs or AEs leading to treatment discontinuation, and will put forward recommendations regarding the study if the benefit-to-risk balance for patients seems to be in jeopardy. The data and the intervals for review will be decided before, or soon after study initiation and documented in the ISC Charter.

The results of FAs will be presented to the ISC, who will decide whether or not the study can continue and whether the enrolment period should be extended.

The organisation of the ISC will be described in the ISC Charter, which will be prepared and approved prior to the first planned FA.

Additional *ad hoc* members may be invited to join the ISC if any safety concerns emerge, in order to give additional support to the competencies already present.

11. Quality Assurance and Quality Control Procedures

The Investigator must maintain appropriate accurate records to ensure that all aspects of conducting the study are fully documented, and that study data can be verified at the end of the study. These documents include the Investigator Site File, the patients' clinical source documents, screening/enrolment logs and other study-specific forms.

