Appendix 5 - Figures

Figure 3 – Statistical Power of the Study

Power of the study depending on the actual difference between the success rates and assuming a success rate of 94% for NECT

The power is improved if the efficacy of NECT is greater than 94%.

The power refers to the probability that the 95% confidence interval of the difference in success rates will exclude the margin of the chosen limit of an unacceptable difference.

The interval between an acceptable difference and an unacceptable difference, as reported by those who responded to the survey, is a "grey area" or a zone of uncertainty.

The Sponsor objective is to have at least an 80% chance of being significant if the actual difference is 5% in favour of NECT, and a very limited chance (1.45% = exact power = exact one-sided type-I error) of being significant if the actual difference is 13%.

Figure 4 – Acceptable and Unacceptable Limits of the Difference in Efficacy at the Testof-Cure Visit

Responses to two questions:

- what is the acceptable margin of difference in efficacy between an oral drug and NECT?
- what is the unacceptable margin of difference in efficacy between the two treatments?

[figure not shown]

Figure 5 – Failure Rate at each Timepoint by Compound

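### The stated 80% power is calculated at one-sided 0.025, not at the Pocock threshold set for the final test (about 74–76%), and the 91.6% in footnote 3 does not hold at 390 patients

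*Protocol*

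**What the plan says.** Section 9.1 revises the sample from 510 to 390 patients, 260 on fexinidazole and 130 on NECT. It begins "If the expected success rates are 94% with NECT and 89% with fexinidazole" and concludes that "the power of the final analysis is 80" per cent with a 13% margin. It adds: "The calculations were made for a one-sided type-1 error of 0.025". The Protocol Summary, under Sample Size, repeats the figure with a different label: "Thus, the overall power is 80% if the actual success rate for NECT is 94% and 89% for fexinidazole".

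Footnote 3 to Section 9.1 takes a second scenario, 0.90 for fexinidazole and 0.95 for NECT, and says that "the exact power of the final primary analysis is 91.6" per cent. It names no sample size. The Summary attributes a power of 87.9% to the former 510 patients.

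Section 9.11 plans an interim test for success on the first 195 patients and states: "The Pocock approach will be used to determine the threshold of significance of the interim analysis as well as that of the final analysis". The protocol gives no number for that threshold.

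The note to Figure 3 (Appendix 5) says: "The power refers to the probability that the 95% confidence interval of the difference in success rates will exclude the margin" of the unacceptable difference. It gives the sponsor's aim as at least an 80% chance of significance when the true difference is 5 points.

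**The concern.** A Pocock boundary spends a substantial part of the error at the interim look, so the final test must pass a stricter threshold than 0.025. Power calculated at 0.025 therefore describes a test that will not be carried out. Section 9.1 and Section 9.11 cannot both apply to the same final analysis if its power is 80%.

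Footnote 3 raises a separate doubt. A move from 94/89 to 95/90 keeps the 5-point difference and reduces the variance only slightly. A rise from 80% to 91.6% is too large for that change at one sample size.

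These figures support the reduction from 510 to 390 patients and the sponsor's stated aim of 80%. Anyone who later interprets a non-significant final result would take the chance of missing true non-inferiority to be smaller than it is.

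**Working it through.** **Inputs.** Group sizes 260 and 130, success rates 94/89 and 95/90, margin 0.13 and one-sided 0.025 (Section 9.1 and footnote 3); Blackwelder test on the difference (Section 9.8.1); interim at 195 of 390 patients and Pocock at both looks (Section 9.11).

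**Step 1: reproduce the 80%.** With unpooled variance:
- SE = √(0.89×0.11/260 + 0.94×0.06/130) = 0.02847
- (0.13 − 0.05)/SE = 0.08/0.02847 = 2.810
- Power at 0.025 = Φ(2.810 − 1.960) = 80.2%

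This is the stated figure, so the 80% is an unadjusted normal-approximation calculation.

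**Step 2: the Pocock threshold.** The assumptions are two looks, information fraction 195/390 = 0.5, total one-sided error 0.025 and correlation √0.5 between the two statistics. Solving P(Z1 > c or Z2 > c) = 0.025 gives c = 2.178, or 0.0147 one-sided at each look.

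**Step 3: power of the final test at that threshold, 94/89.**
- Normal: Φ(2.810 − 2.178) = 73.6%
- Exact (full binomial enumeration of the uncorrected test): 75.7%, against 82.3% at 0.025

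Like for like, the adjustment costs 6.6 points on either method (80.2 − 73.6; 82.3 − 75.7).

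**Step 4: success at either look, 94/89.** This treats the 12-month and 18-month success rates as equal. The expected interim statistic is 2.810 × √0.5 = 1.987, so interim power is Φ(1.987 − 2.178) = 42.4%. The bivariate normal gives 75.9% for success at either look. Simulation with binomial data gives 77.7% for the uncorrected Wald test and 78.1% for the Farrington–Manning test.

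**Step 5: the 91.6%, 95/90.**
- SE = √(0.90×0.10/260 + 0.95×0.05/130) = 0.02667, and 0.08/SE = 2.999

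| 390 patients, 95/90 | one-sided 0.025 | one-sided 0.0147 |
|---|---|---|
| Normal | 85.1% | 79.4% |
| Exact, uncorrected | 86.7% | 81.2% |
| Exact, continuity-corrected | 81.3% | 74.8% |

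No entry reaches 91.6%. With 340 and 170 patients (510 at 2:1) and 0.025, the exact power of the continuity-corrected test is 91.6%. The same method at 94/89 gives 87.8%, close to the 87.9% that the Summary attributes to 510 patients.

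**The case against.** **Overall power may mean success at either look.** The Summary's wording allows this, and the shortfall is then smaller: 75.9% to 78.1%. If the two statistics are less correlated than √0.5, which is possible because the interim uses a 12-month endpoint with its own imputation rule, the normal figure rises to 77.2% (correlation 0.6) or 78.5% (correlation 0.5), with the threshold held at 2.178. It stays below 80%, and Section 9.1 attaches the same 80% to the final analysis. This objection narrows the gap but does not close it.

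**The 1.45% error under Figure 3 might suggest that Pocock was already applied.** It is an exact size at a true 13-point difference. The continuity-corrected test at nominal 0.025 has size 1.42% with 390 patients and 1.52% with 510, so 1.45% is no evidence of adjustment. Of the test versions tried at 0.0147 with 390 patients, the largest final-test power is 75.9% (Farrington–Manning).

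**The numerical threshold can be left to the SAP.** This stands, and its absence from the protocol is not the complaint. The complaint is that the printed powers disagree with the protocol's own error rule and sample size.

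**Two stronger readings are not supported.** A reader might infer from Section 9.8.1, where the 95% "confidence interval will prevail over interpretation of the test result in assessing the benefit-to-risk balance", that a 95% interval replaces the adjusted test and undoes the Pocock correction. That sentence concerns benefit-to-risk interpretation. Section 9.8.1 names the Blackwelder test as primary and Section 9.11 sets its threshold, so the adjusted test remains the decision rule. A reader might also set the continuity-corrected 68.6% (94/89 at 0.0147) against the stated 80%. That mixes two changes, because the corrected test already has only 76.0% at 0.025.

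**Conclusion.** The point holds. For 94/89 with 260 and 130 patients, the 80% is valid only at an unadjusted one-sided 0.025. At the Pocock threshold, the final test has about 74% (normal) or 76% (exact), a shortfall of roughly 4 to 6 points against the stated figure. Success at either look has about 76–78%. The sponsor's aim of at least 80% at a 5-point difference is therefore not met by the final test as specified.

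The 91.6% for 95/90 is wrong for 390 patients: too high by about 5 to 6.5 points at 0.025 (against 86.7% exact and 85.1% normal) and by about 10 to 12 points at the Pocock level (against 81.2% and 79.4%). That it comes from the 510-patient design is an inference from two numerical matches, one of them 0.1 point off; the protocol does not say so.

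The 0.0147 rests on looks at exactly 195 and 390 patients and a total one-sided error of 0.025. The either-look figures also require equal success rates at 12 and 18 months. The footnote's claim of more than 99% power for equal success rates is not affected: it is at least 99.6% at 390 patients under the Pocock threshold. The planned control of type-I error is not in question either; the fault lies in the stated power.

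**What to change.** Keep 390 patients. In the Summary, Section 9.1, footnote 3 and Figure 3:
- State the Pocock per-look threshold (about one-sided 0.0147 under the assumptions above) and the version of the Blackwelder test used for the power figures.
- Restate the power of the final test as about 74% for 94/89 and about 79% for 95/90 (normal approximation), and remove the 91.6%.
- Give the either-look power separately, about 76% for 94/89 by the same approximation, with its assumption of equal 12- and 18-month rates, and use the term overall power only for that quantity.
- Base Figure 3's definition of power on the adjusted threshold. Its present 95% interval corresponds to one-sided 0.025.

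The cost is protocol and SAP wording, with a less favourable stated power. No patients, visits or analyses are added. For scale, 80% at 94/89 under the Pocock threshold would need about 453 patients for the final test, or about 432 for success at either look (normal approximation). The sponsor would be accepting the lower power knowingly.

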⁴ Three logistic models were fitted to MSF data: one using the baseline and 6-month CSF WBC counts, as well as the age and sex of the patient (significant explanatory variables); another using 6-month and 12-month CSF WBC counts; and the last one using the CSF WBC count at 12 months, age and sex. The rate of false positives was 3.3% and the rate of false negatives was 3.0% for patients having a WBC count at 6 and 12 months after EOT. These models provide the probability of being cured at 24 months. The outcome is assessed at 24 months instead of 18 months because most patients in the MSF database had a missing CSF WBC count at 18 months. It is assumed that if cure at 24 months can be adequately predicted using the model, the prediction of cure at 18 months should be conservative due to possible relapses between 18 and 24 months.

⁵ This approach assumes that the predicted probability of success is not dependent on whether or not patients are lost to follow-up in the study. This assumption seems realistic since, in most

patients at 18 months or later, in order to establish whether the outcome is a success because the primary analysis is not based on this rule. Cases that do not comply with the protocol but in which the outcome is known at any time after 18 months will be used in the efficacy analyses. The models will be validated in a blinded manner once all randomised patients have reached the 18-month visit after the EOT (primary endpoint).

Analysis	Method of imputation
Primary	Primary method (method similar to Priotto)
1 st sensitivity analysis	Fourth method: surrogate endpoint (predicted or actual outcome)
2 nd sensitivity analysis (treatment completers)	Primary method
3 rd sensitivity analysis (evaluable patients)	Primary method
4 th sensitivity analysis (per protocol population)	Fourth method
5 th sensitivity analysis	Second method (patient lost to follow-up = failure)
Planned secondary analysis (K-M analysis)	Third method

For the interim analysis, if the lumbar puncture is missing at M12:

- if a lumber puncture was performed at M18, the result at M18 will be used,
- o if a lumber puncture was performed at M6, success will be imputed if the WBC count is ≤ 5/µL, no trypanosomes are detected and no symptoms related to HAT are present at 12 months,
- if data for lumbar puncture are available at M6 and at M18, the outcome at M18 will prevail.

All other cases in which the lumbar puncture is missing will be considered as failures.

9.3. Handling of Centres

The primary analysis will not be stratified by centre. However, a logistic model with random intercepts using the centre and treatment as covariables will be used to check whether there is an interaction between the centre and the treatment, and whether there is a main centre effect. If there is a significant centre effect, the primary analysis may be slightly biased because of the dependency among observations. The odds ratio of success will provide an estimate of the treatment effect, and the odds ratio margin will be calculated *a posteriori* based on the

cases, patients who choose not to attend follow-up visits do so because they are doing well.

success rate with NECT minus 13%. If there is a significant interaction, it will not be possible to generalise the estimate of the treatment effect. The centre(s) responsible for the interaction will be examined.

The analysis stratified by centre is a secondary analysis. This secondary analysis provides an estimate of the odds ratio of success and the predicted success rate of each treatment, with a 95% confidence interval, but not the excess of the success rate.

Туре	Aim	Definition	
Primary: ITT patients	Analysis of safety and primary efficacy analysis	All randomised patients who received at least one dose of study treatment.	
		Except patients who fled an area of armed conflict and for whom no post-treatment data are available (these patients will be included in the population as failures for a sensitivity analysis).	
Secondary: treatment completers	Sensitivity analysis on efficacy	All randomised patients who completed the treatment period and who received all protocol-planned doses.	
Secondary: evaluable patients	Sensitivity analysis on efficacy	ITT patients, except those who died due to causes clearly unrelated to efficacy or safety. Exclusion will be documented and decided during the blind data review.	
Secondary: per protocol patients	Sensitivity analysis on efficacy	ITT patients with no major protocol violations. Major violations will be provided for each patient, and exclusion will be decided during the blind data review.	

9.4. Definition of Study Populations included in the Analyses Populations used in the analyses

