9.8. Efficacy Analysis

9.8.1. Primary Efficacy Analysis

Primary Efficacy Endpoint

The primary efficacy endpoint is the outcome at 18 months. Outcome will be considered as a success if there is no evidence of trypanosomes in any bodily fluid and if the CSF WBC is $\leq 20/\mu$ L. Death and use of rescue treatment will be considered as a relapse, i.e. a failure. A patient who attends the 18-month visit or who is found again after an active search, who refused to undergo lumbar puncture but who has no signs or symptoms of HAT, and for whom the outcome was assessed as favourable at the latest assessment will be considered as a probable cure, i.e. a success, unless signs of relapse are detected on any assessment up to 24 months.

Primary Assessment Criterion

The primary assessment criterion is the success rate at 18 months.

Primary Test

The primary test is the Blackwelder non-inferiority test, based on the difference in the success rates and a margin of 13% (see Margin for "Acceptable Difference"; p 63).

Primary Measure of Size of Effect

The size of the treatment effect will be measured by the excess rate of success. The excess success rate is equal to the difference in the success rates between the two groups: size of effect = p_{fexi} - p_{NECT} . A negative success rate corresponds to a treatment effect in favour of NECT.

Margin for "Acceptable Difference"

The margin for an "acceptable difference" is set at $13\%^6$.

⁶ A survey was carried out by e-mail in the small population of local and international physicians who are experienced in treating patients with HAT, in order to assess the limit of an acceptable difference and the limit of an unacceptable difference in efficacy between an oral drug and NECT. Between the two limits, there is an "uncertainty zone". The median response for an unacceptable difference was 17% and the median response for an acceptable difference was 9%. A margin of 13% was chosen and is equal to the first tertile of the distribution of an unacceptable difference. It means that the unacceptable limit was above 13% for 2/3 of respondents, i.e. for 6/19 respondents, the unacceptable limit was below 13% and, for 12/19, the limit was above 13%. The margin of 13% is also at the mid-point between the median of an acceptable difference (9%) according to respondents and the median of an unacceptable difference (17%) for the same respondents (see results of the survey in Figure 4; p 108).

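### The centre-adjusted check in 9.3 uses an odds ratio against a data-derived margin and gives no adjusted risk difference; on its natural reading it often fails to confirm a positive primary result

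*Protocol*

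**What the plan says.** Section 9.8.1 puts the primary claim on the difference scale: "The primary test is the Blackwelder non-inferiority test, based on the difference in the success rates and a margin of 13" per cent. The effect measure there is also the difference in success rates.

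Section 9.3 leaves the primary analysis unstratified and adds "a logistic model with random intercepts using the centre and treatment as covariables" to look for a centre effect and a centre-by-treatment interaction. It warns: "If there is a significant centre effect, the primary analysis may be slightly biased because of the dependency among observations". The next sentence turns to the odds ratio of success as the estimate of the treatment effect and says that "the odds ratio margin will be calculated" a posteriori, based on the "success rate with NECT minus 13" per cent.

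The section then gives the status and output of this work. "The analysis stratified by centre is a secondary analysis", and it yields the odds ratio and the predicted success rate of each treatment "with a 95% confidence interval, but not the excess of the success rate".

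**The concern.** A reader who wants to know whether non-inferiority survives adjustment for centre gets no interval on the scale of the primary test. What 9.3 offers is an odds ratio and a margin that moves with the observed NECT rate. An odds-ratio margin has one evident use, which is to be compared with the interval of the odds ratio. If that comparison is badly calibrated, a trial with a clear primary result and some variation between centres could report that the adjusted analysis does not support non-inferiority, for reasons unrelated to centres or to the drug. Table 7 lists ten sites with expected totals of 7 to 86 patients, so a centre effect is a realistic prospect.

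**Working it through.** **Inputs.** Section 9.1: 260 fexinidazole and 130 NECT patients, expected success 89% and 94%, margin 13%, one-sided 0.025, stated power 80%. The footnote there adds the pair 95% and 90%. Section 9.3 gives the basis of the odds-ratio margin and the 95% interval.

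**Reproducing the plan's figure.** The unpooled standard error of the difference is √(0.94×0.06/130 + 0.89×0.11/260) = 0.0285. Then (0.13 − 0.05)/0.0285 − 1.96 = 0.85, so power is 80.2%. This matches the stated 80%. Exact enumeration of the same test gives 82.3%.

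**The rule examined.** With pN the observed NECT rate,

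margin = [(pN − 0.13)/(1 − pN + 0.13)] / [pN/(1 − pN)].

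Non-inferiority is confirmed if the lower 95% Wald limit of the odds ratio lies above this margin, treated as a constant. The margin is 0.372 at pN = 90%, 0.272 at 94% and 0.162 at 97%. That movement is not itself an error: it is what a constant 13-point difference implies on the odds scale.

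**Why it is too strict.** On the log scale, with pF the observed fexinidazole rate,

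log OR − log margin = logit(pF) − logit(pN − 0.13).

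The NECT logit cancels, but the standard error of the log odds ratio still charges its full variance.
- NECT part charged, at 94%: √(1/(130×0.94×0.06)) = 0.369.
- Actual SD of logit(pN − 0.13): √(0.94×0.06/130)/(0.81×0.19) = 0.135.

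**Exact results** (all 261 × 131 outcomes, no centre effect, one-sided 0.025):

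| True NECT / fexinidazole | Risk-difference test positive | Odds-ratio rule positive | Odds-ratio rule fails, given positive primary |
|---|---|---|---|
| 94 / 81 (type-I error) | 2.3% | 0.14% | 94% |
| 94 / 89 | 82.3% | 26.7% | 67.5% |
| 95 / 90 | 86.8% | 25.1% | 71.1% |
| 94 / 91 | 96.8% | 52.6% | 45.6% |
| 94 / 92 | 99.1% | 66.5% | 32.8% |
| 94 / 94 | 100% | 88.2% | 11.8% |

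**Worked example at about the expected counts** (122/130 and 231/260). The difference is −5.0 points with lower limit −10.6, so the primary test is positive. The odds ratio is (231/29)/(122/8) = 0.52, 95% interval 0.23 to 1.18. The margin is 0.277, so the odds-ratio rule fails.

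**Separating the two causes, at 94/89.**
- Carrying the margin's sampling error into the comparison: power 79.6%, and 3.3% of positive primary results not confirmed.
- Fixing the margin in advance at 0.272: type-I error 3.0%, but power only 33.6%, and 59% of positive primary results not confirmed.

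Ignoring the margin's sampling error spoils the error rate. The odds-ratio scale costs power even with a fixed margin.

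**With centres in the model.** A random-intercept logistic model was simulated with the ten Table 7 site sizes, 800 runs per scenario, and assumed between-centre SDs of 0, 0.5 and 1.0 on the logit scale. At 94/89 the rule failed in 68%, 70% and 73% of trials with a positive primary result; at 94/94, in 11% to 14%. The problem does not come from leaving centres out of the enumeration.

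**The case against.** The strongest reply is that 9.3 states no test. It calls the odds ratio an estimate, names no rejection rule and does not say that the margin is taken as a constant; section 9 leaves detailed methods to an SAP that is not shown. This matters, because carrying the margin's sampling error removes nearly all the disagreement. It stands as a condition on the figures, which hold for the natural reading only. It does not remove the stated exclusion of the adjusted risk difference.

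A reader might also infer that the odds-ratio result would contradict or replace a positive primary result. The documents do not support that. The analysis is secondary, 9.3 speaks only of slight bias, and 9.8.2 says the centre analyses serve mainly to judge generalisability, and also possible bias in the confidence interval. Section 9.8.1 puts the effect size and its interval above the test result. A wide interval that includes the margin is a failure to confirm, not evidence of inferiority. The error is conservative, so no false claim of non-inferiority follows.

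Nor can one say without condition that the check would usually fail. It does so at the planning rates and for true deficits of about 4 points or more (57.5% at 94/90), but not when the two drugs are close.

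Finally, 9.3 does report predicted success rates with intervals. That helps description, but separate intervals for two rates do not give an interval for their difference.

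**Conclusion.** The point holds as a defect in a secondary analysis. Section 9.3 leaves the scale of the primary claim exactly where a centre-adjusted check is wanted, and the margin it supplies leads to a poorly calibrated comparison. If the 95% interval of the odds ratio is set against the a posteriori margin as a constant, type-I error is about 0.14% instead of 2.5%, power at 94/89 is about 27% against 82%, and about two thirds of positive primary results there go unconfirmed. The share falls to 12% if the true rates are equal.

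The figures assume that reading, a Wald interval, the observed NECT rate as the base of the margin, and 260 and 130 analysed patients. They use the 95% interval that 9.3 specifies. The Pocock adjustment in 9.11 is not applied, because the protocol gives no figure for it and does not attach it to this analysis. The primary verdict is unaffected; what is at risk is a spurious failure to confirm when centres differ.

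**What to change.** In 9.3, replace the odds-ratio margin with a centre-adjusted risk difference and its 95% interval, judged against the same 13% margin. Either a Mantel-Haenszel weighted difference across centres with a suitable interval (for example of Newcombe or Miettinen-Nurminen type) or a difference standardised from the logistic model would do. Delete the statement that the excess success rate is not provided. Keep the odds ratio as a descriptive measure, with no a posteriori margin. Merely fixing the odds-ratio margin in advance is not enough, because most of the power loss remains.

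The cost is a change of wording and one extra standard analysis. With sites expected to recruit as few as 7 patients, small centres may need pooling, and the pooling rule should be set before unblinding.
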